2. SYNOPSIS

Study Title	A multi-centre, randomised, controlled non-inferiority trial to compare the efficacy, safety and tolerability of Triple Artemisinin-based Combination Therapies versus first-line ACTs + placebo for the treatment of uncomplicated Plasmodium falciparum malaria in Africa
ACRONYM	DeTACT-Africa
Trial Design	A partially blinded randomised controlled non-inferiority trial comparing the efficacy, tolerability and safety of Triple ACTs artemether-lumefantrine+amodiaquine (AL+AQ) and artesunate-mefloquine+piperavaquine (ASMQ+PPQ) and the ACTs artemether-lumefantrine+placebo (AL+PBO), artesunate-mefloquine+placebo (ASMQ+PBO) (with single-low dose primaquine in some sites) for the treatment of uncomplicated Plasmodium falciparum malaria to assess and compare their efficacy, safety, tolerability.
Trial Participants	Subjects with acute uncomplicated P. falciparum malaria
Sample size	Estimated total sample size up to 3240 subjects recruited at 8 sites in Africa (Burkina Faso, DRC, The Gambia, Guinea, Niger, Nigeria, Rwanda, Tanzania) 
 - In Rwanda only – 216 subjects - All other sites – 432 subjects per site
Inclusion Criteria	
 • Male or female, aged ≥ 6 months to < 12 years (For Gambia, Rwanda sites only: ≥ 6 months) • Ability to take oral medication • Acute uncomplicated P. falciparum mono-infection • Asexual P. falciparum parasitaemia: 1,000/μL to $\leq 10\%$ parasitaemia, determined on a peripheral blood film (At Gambia, Rwanda sites only: For subjects ≥ 12 years – 1000/μL to 200,000/μL) • Fever defined as $\geq 37.5^{\circ}\text{C}$ tympanic temperature or a history of fever within the last 24 hours • Written informed consent by the subject or by the parent/guardian in case of children lower than the age of consent and assent if required (per local regulations) • Willingness and ability of the subjects or parents/guardians to comply with the study protocol for the duration of the study

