
Drugs
 
See Appendix 2 for dosing regimens
	
In Rwanda only:
 
Artemether-lumefantrine+placebo for 3 days.
 
VERSUS
 
Artemether-lumefantrine+amodiaquine for 3 days.
 
All other sites:
 
Artemether-lumefantrine+placebo for 3 days.
 
VERSUS
 
Artemether-lumefantrine+amodiaquine for 3 days.
 
VERSUS
 
Artesunate-mefloquine+placebo for 3 days
 
VERSUS
 
Artesunate-mefloquine+piperavaquine for 3 days
 
Primaquine
 
According to the WHO guideline, all subjects except children under 10 kilograms will also be treated with a single dose of primaquine according to the local requirements or guidelines and WHO treatments schedule as a gametocytocidal treatment. Primaquine will not be deployed in study sites with median to high levels of malaria

	transmission (estimated Annual Parasite Incidence (API) \geq 50 per 1000 population per year according to the WHO World Malaria Report 2017)
--	--

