7. PROPOSED ACTIVITIES

Subjects will be randomized to up to four arms: artemether-lumefantrine + amodiaquine, artemether-lumefantrine + placebo, artesunate-mefloquine + piperazine and artesunate-mefloquine + placebo. As a contingency measure in case of significant differences in the efficacy or safety of one of the combinations being tested and/or study drug expiry or unavailability, subjects may be randomized to 2 arms with a matching ACT-TACT pair, i.e., with artemether-lumefantrine + placebo or artemether-lumefantrine + amodiaquine OR artesunate-mefloquine + placebo or artesunate-mefloquine + piperazine.

Some sites may randomize between 2 arms only with matching ACT-TACT pairs, i.e., artemether-lumefantrine + placebo or artemether-lumefantrine + amodiaquine OR artesunate-mefloquine + placebo or artesunate-mefloquine + piperazine. In Rwanda, subjects will be randomized between 2 arms consisting of artemether-lumefantrine + placebo or artemether-lumefantrine + amodiaquine.

In the control arms, the ACT will be co-packed with a matched (appearance) placebo.

In lower transmission settings (Annual Parasite Incidence <50 per 1000 population per year) the treatment will include a single 0.25 mg/kg gametocytocidal dose of primaquine as recommended by the WHO for children ≥ 10 kg. All drug administrations will be observed.

Subjects will be treated in an in-patient unit for 3 days and followed up weekly up to D63. Microscopy to detect and quantify malaria parasitaemia will be performed daily (more frequently in patients with parasite density of $>5000/\mu\text{L}$ at inclusion) during hospitalization, at all weekly and unscheduled visits. A physical examination and measurements of vital signs along with a symptom questionnaire for tolerability will be performed and recorded through a standardized method at baseline, daily during admission and weekly during follow up through D42 and at all unscheduled visits. Physical exam, vital sign measurements and assessments of symptoms will be performed on D49, D56, and D63 only for patients who are parasitaemic or those who report fever or other symptoms. Electrocardiographs will be performed during admission (H0, H4, H52 or H64) and day 42 of follow up to assess and compare the effect of ACTs and TACTs antimalarials on QT or QTc intervals.

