8.2. Inclusion criteria

- Male or female, aged ≥ 6 months to < 12 years (For Gambia, Rwanda sites only: ≥ 6 months)
- Ability to take oral medication
- Acute uncomplicated *P. falciparum* mono-infection
- Asexual *P. falciparum* parasitaemia: 1,000/ μ L to $\leq 10\%$ parasitaemia, determined on a peripheral blood film (For Gambia, Rwanda sites only: For subjects ≥ 12 years – 1000/ μ L to 200,000/ μ L)
- Fever defined as $> 37.5^{\circ}\text{C}$ tympanic temperature or a history of fever within the last 24 hours
- Written informed consent by the subject or by parent/guardian in case of children lower than the age of consent and assent if required (per local regulations)
- Willingness and ability of the subjects or parents/guardians to comply with the study protocol for the duration of the study

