10. STUDY DRUG

10.1. Study drug regimens

Overview DeTACT drug regimens	
TACT-arm	ACT-arm
In all sites	
Artemether -lumefantrine x 3 days PLUS Amodiaquine x 3 days	Artemether -lumefantrine x 3 days PLUS Placebo x 3 days
In all sites except Rwanda	
Artesunate -mefloquine x 3 days PLUS Piperaquine x 3 days	Artesunate -mefloquine x 3 days PLUS Placebo x 3 days
In low transmission settings subjects will receive a single low dose primaquine on day 1 according to the WHO guidelines and local regulations	

Subjects will be treated with weight-based doses according to the schedule in appendix 2.

The study drugs will be administered by study medical or nursing staff while the subjects are hospitalised.

The study drugs containing artemether-lumefantrine+/-placebo will be taken with at least 1.2 grams of fat to optimize absorption (comparable to 80-100 ml of a MILO milk carton or an equivalent fat containing beverage or snack).

No meals or snacks must be consumed for 1 hour before and after intake of study drugs containing artesunate-mefloquine+/-piperaquine. In case any food is taken, it must be non-fatty snacks (e.g., small quantity of rice, bread, crackers, etc.)

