10.6.6. Primaquine

Primaquine is available in tablets of 7.5 and 15 base mg. The weight-based treatment schedule in appendix 2 aims for a dosage of approximately 0.15-0.375 mg/kg on day one thereby approaching the 0.25 mg base/kg single dose recommended by the WHO.

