26. APPENDIX 2. DOSING SCHEDULES

Artemether-lumefantrine + amodiaquine or placebo

Artemether-lumefantrine + Amodiaquine (or placebo) dosing schedule			
Body weight (kg)	Dose administered at 0h, 8h, 24h, 36h, 48h, 60h		
	Artemether (mg)	Lumefantrine (mg)	Amodiaquine (mg) / PBO
5 to 9.9	20	120	40 / 0
10 to 15.9	40	240	80 / 0
16 to 29.9	60	360	120 / 0
30 to 54.9	100	600	200 / 0
≥ 55	120	720	240 / 0

Artemether-lumefantrine +/- Amodiaquine (or placebo) dosing schedule		
One tablet of AL contains 20 mg artemether and 120 mg lumefantrine; One tablet of AQ contains 40 mg amodiaquine; Placebo contains no active pharmaceutical ingredient.		
Body weight (kg)	Number of tablets per timepoint (0h, 8h, 24h, 36h, 48h, 60h)	
	AL	Amodiaquine / PBO
	Tablets	Tablets
5 to 9.9	1	1
10 to 15.9	2	2
16 to 29.9	3	3
30 to 54.9	5	5
≥ 55	6	6

Artesunate-mefloquine + piperazine or placebo

Artesunate-mefloquine + piperazine (or placebo) dosing schedule			
Body weight (kg)	Dose administered at 0h, 24h, 48h		
	Artesunate (mg)	Mefloquine HCl (mg)	Piperazine TP (mg) / PBO
5 to 10.9	32	70	160 / 0
11 to 17.9	64	140	320 / 0
18 to 33.9	100	220	500 / 0
34 to 64.9	200	440	1000 / 0
≥ 65	300	660	1500 / 0

Artesunate-mefloquine + piperazine (or placebo) dosing schedule			

One Paediatric tablet of AS contains 32 mg artesunate, one Adult tablet contains 100 mg; One Paediatric tablet of MQ contains 70 mg mefloquine, one Adult tablet contains 220 mg; One Paediatric tablet of PPQ contains 160 mg piperazine, one Adult tablet contains 500 mg; Paediatric and Adult placebos contain no active pharmaceutical ingredient.
			
Body weight (kg)	Number of tablets per timepoint (0h, 24h, 48h)		
	Artesunate	Mefloquine HCl	Piperazine TP / PBO
	Tablets	Tablets	Tablets
5 to 10.9	1 (Paed)	1 (Paed)	1 (Paed)
11 to 17.9	2 (Paed)	2 (Paed)	2 (Paed)
18 to 33.9	1 (Adult)	1 (Adult)	1 (Adult)
34 to 64.9	2 (Adult)	2 (Adult)	2 (Adult)
≥ 65	3 (Adult)	3 (Adult)	3 (Adult)

Primaquine

Primaquine dosing schedule			
One tablet of Primaquine contains either 7.5 or 15 mg of Primaquine			
Body weight (kg)	Dose administered at 24 h		
	Primaquine (mg)	7.5 mg tablet	15 mg tablet
<25	3.75	0.5	0.25
25 – 50	7.5	1	0.5
>50	15	2	1

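### The lowest row of the Appendix 2 primaquine table has no lower weight limit, so it assigns a dose to children under 10 kg, whom the protocol excludes from primaquine

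*Protocol*

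**What the plan says.** **Who gets primaquine.** The protocol states the weight rule twice, the same way each time. Under Drugs in the synopsis: "all subjects except children under 10 kilograms will also be treated with a single dose of primaquine". Section 7 (Proposed activities) specifies "a single 0.25 mg/kg gametocytocidal dose of primaquine as recommended by the WHO for children" of 10 kg and above, in settings with annual parasite incidence below 50 per 1000. The trial-design entry of the synopsis adds the qualifier "with single-low dose primaquine in some sites".

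**How much they get.** The synopsis points to Appendix 2 for dosing regimens. Section 10.1 (Study drug regimens) says: "Subjects will be treated with weight-based doses according to the schedule in appendix 2". Section 10.6.6 (Primaquine) says the Appendix 2 schedule "aims for a dosage of approximately 0.15-0.375 mg/kg on day one", around a recommended 0.25 mg/kg.

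**What the table prints.** The lowest primaquine row in Appendix 2 reads "<25 3.75 0.5 0.25", meaning below 25 kg, 3.75 mg, half a 7.5 mg tablet or a quarter of a 15 mg tablet. It has no lower weight, footnote or exclusion row. The next rows are 25-50 kg (7.5 mg) and above 50 kg (15 mg).

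**The neighbouring tables.** Appendix 2 has four other weight tables, two for artemether-lumefantrine with or without amodiaquine and two for artesunate-mefloquine with or without piperaquine. All four start at 5 kg. The first artemether-lumefantrine row, for example, is "5 to 9.9 20 120 40 / 0".

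**The concern.** The eligibility text and the dosing table disagree for children under 10 kg: the text withholds primaquine from them, while the table, read as printed, gives them 3.75 mg.

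The gap is in the part of the protocol that staff would use when giving the drug. The 10 kg limit appears in the synopsis and section 7 only. Section 10, which governs dosing, does not repeat it: its regimen table says that subjects in low-transmission settings receive primaquine, and neither section 10.1 nor section 10.6.6 states a weight limit.

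The trial expects such children. Most sites enrol "Male or female, aged ≥ 6 months to < 12 years", and The Gambia and Rwanda also start at 6 months. The lowest artemether-lumefantrine band (5 to 9.9 kg) lies wholly below the primaquine limit. The lowest artesunate-mefloquine band (5 to 10.9 kg) straddles it, so the partner-drug band cannot stand in for a primaquine floor. Section 9.10 (Blood volumes) even has a separate sampling rule for children below 6 kg.

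At stake is an avoidable dosing error in small children at any site that uses primaquine. A second effect would be on the exploratory objective on haemolysis after single low-dose primaquine, which would pick up exposures outside the intended schedule.

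**Working it through.** **Inputs**

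- Doses by weight band (Appendix 2, Primaquine): below 25 kg, 3.75 mg; 25-50 kg, 7.5 mg; above 50 kg, 15 mg.
- Aimed-for range: about 0.15-0.375 mg/kg (section 10.6.6).
- Target: 0.25 mg/kg (sections 7 and 10.6.6).
- Weight limit: 10 kg (synopsis and section 7).
- Lowest weight in the partner-drug tables: 5 kg (Appendix 2).

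**Formula.** Dose in mg/kg = tablet dose in mg / body weight in kg.

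**Step 1. Reproduce the protocol's range with a 10 kg floor.**

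- First row: 3.75/10 = 0.375 at the bottom; 3.75/25 = 0.150 at the top.
- Second row: 7.5/25 = 0.300 and 7.5/50 = 0.150.
- Third row, at its lower edge: 15/50 = 0.300.

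This gives 0.15-0.375 mg/kg, the stated range. The lower end, 0.15, arises with or without a floor (7.5/50). The upper end does not: the second and third rows never exceed 0.300, so 0.375 can come only from the first row, at exactly 10 kg. The section that describes the table therefore already assumes the floor that the table omits.

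**Step 2. Apply the row as printed to children under 10 kg.** The row passes 0.375 mg/kg at 3.75/0.375 = 10 kg, so every child below 10 kg would be above the aimed-for range.

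| Weight (kg) | mg/kg from 3.75 mg | Ratio to 0.375 (upper end) | Ratio to 0.25 (target) |
|---|---|---|---|
| 10 (eligible) | 0.375 | 1.00 | 1.50 |
| 9.9 | 0.379 | 1.01 | 1.52 |
| 8 | 0.469 | 1.25 | 1.88 |
| 6 | 0.625 | 1.67 | 2.50 |
| 5 | 0.750 | 2.00 | 3.00 |

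**Step 3. Check the proposed row.** Labelled 10 to <25 kg, the first row runs from 0.375 mg/kg at 10 kg to 3.75/24.9 = 0.151 mg/kg at 24.9 kg, which lies inside the range in section 10.6.6.

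**The case against.** The strongest reply is that this is an omission, with no real conflict over who should be treated. Eligibility is set in the synopsis and section 7; Appendix 2 only says how much an eligible child receives; and nothing in the protocol says that a child under 10 kg should have primaquine. The range in section 10.6.6 confirms the intention. Harm also needs several conditions together: a site that uses primaquine, a child under 10 kg enrolled there, and staff who dose from the table alone. Dosing is by study staff in hospital and is observed.

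Much of this stands. The intended rule is clear, the harm is conditional, and the documents do not say that these doses are harmful. Near the limit the excess is trivial: 0.379 mg/kg at 9.9 kg is not meaningfully outside a range described as approximate. The protocol also accepts 1.5 times the target in an eligible 10 kg child, so a multiple of the target alone does not mark an error. The 2.0 and 3.0 multiples apply only at 5 kg.

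It does not dispose of the point. Observed dosing ensures that the scheduled dose is swallowed; it does not correct the schedule. An approximate range does not stretch to a doubling. A paediatric dosing table should not depend on staff recalling a limit stated in another section.

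One could also say that section 10.1 needs the same correction, since its primaquine line names no weight limit. That line defers to WHO guidelines and local regulations, and section 10.1 takes its weight-based doses from Appendix 2. An explicit exclusion row there settles section 10.1 as well.

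**Conclusion.** The concern holds. The lowest primaquine row in Appendix 2 has no floor, is the only weight table in the appendix without one, and as printed covers children whom the synopsis and section 7 exclude. The fault is in the dosing row; the eligibility rule itself is consistent.

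For a child under 10 kg dosed from the table, the dose would run from just above the aimed-for range near 10 kg to twice its upper end at 5 kg. The 5 kg end assumes the lowest weight that the partner-drug tables provide for; the documents give no weight distribution below 10 kg.

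The number of children affected cannot be derived and may be nil, because the documents do not say which sites will use primaquine or how many children under 10 kg those sites will enrol. Sample size, type I error and the primary endpoint and its analysis are untouched. This is a correction for participant safety and protocol adherence, worth making because it costs almost nothing.

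**What to change.** In the Appendix 2 primaquine table:

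1. Relabel the lowest row as 10 to <25 kg, keeping 3.75 mg and the tablet fractions.
2. Add a row above it: <10 kg, no primaquine.

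No other section needs to change. The cost is one row label and one added row, with no effect on design, sample size or analysis.

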3. BACKGROUND, RATIONALE AND PROJECT STRUCTURE

3.1. Background

Artemisinin combination therapies (ACTs) have been a major contributor to the substantial reductions in global malaria morbidity and mortality over the last decade. However, further gains are threatened by the recent emergence of artemisinin and partner drug resistance in Southeast Asia, a region which has been the epicentre for the evolution and spread of resistance to every important class of antimalarials.

The Tracking Resistance to Artemisinin Collaboration (TRAC), coordinated by the Mahidol Oxford Research Unit (MORU) at sites in Asia and Africa, mapped areas of artemisinin resistance, defined as slow parasite clearance (clearance half-life >5 hours) [1]. In many areas with artemisinin resistance, this has now been compounded by ACT partner drug resistance [2]. Consequently, treatment failures after artemisinin combination therapies are becoming more widespread in Southeast Asia. Failure rates of >60% for dihydroartemisinin-piperaquine have been documented in Cambodia, Thailand and Vietnam [3-5], (TRACII project unpublished data).

A lineage of artemisinin and piperaquine resistant parasites originating in Western Cambodia is now well established in Cambodia, Vietnam and Thailand [6]. In Cambodia, the first line treatment for uncomplicated *P. falciparum* malaria has recently been changed to artesunate-mefloquine, but it is feared that the current high efficacy of this combination can be lost rapidly.

Loss of efficacy of first line ACTs jeopardizes current malaria control and elimination efforts and will accelerate the spread of drug resistance. A major concern is that artemisinin and partner drug resistance may spread across a wider geographic area, as chloroquine resistance did in the 1960s and 1970s, moving from Southeast Asia to the Indian subcontinent and subsequently to Africa, which bears the vast majority of the global malaria burden. Furthermore, artemisinin resistance could worsen by extending beyond the current ring stage parasite resistance, although this has until now not been observed.

New antimalarial drugs are not expected to come to the market within the next 5 years. There is an urgent need to evaluate alternative treatments using combinations of existing drugs which will not fall rapidly to resistance and can be deployed immediately. These treatments are needed now for areas in the Greater Mekong Subregion where ACTs are increasingly failing. In addition, regions where ACTs are currently still effective, including Myanmar, Bangladesh, India and Sub-Saharan Africa, will need to be prepared with alternative treatments in case multidrug resistant *falciparum* malaria is imported or emerges *de novo*. For these regions it is important to develop strategies to prevent the spread or delay the emergence of artemisinin and ACT partner drug resistance and deployment of Triple Artemisinin Combination Treatments (TACT) could be part of such a strategy.

The underlying scientific rationale for TACTs is similar to that underlying current ACTs and the treatment of tuberculosis, Human Immunodeficiency Virus, *Helicobacter pylori*, and several other infections. If drugs with different targets or resistance mechanisms are combined, then the

probability that resistance will emerge to the combination will usually equate to the product of the individual components' resistance probabilities. As these individual probabilities are very small, combining drugs is a powerful method of reducing the emergence of resistance [7]. The emergence and survival of a mutant organism which is spontaneously (i.e. *de novo*) resistant to two or more drugs is rare.

There appears to be a fortuitous inverse relationship between the resistance mechanisms to lumefantrine and amodiaquine. A similar inverse relationship might exist for piperazine and mefloquine. Furthermore both drug pairs have reasonable well matched elimination kinetics providing mutual protection against resistance throughout the elimination phase of the remaining parasitaemia. Evidence supporting the counteracting resistance mechanisms of amodiaquine versus lumefantrine and piperazine versus mefloquine comes from molecular genetic and genetic epidemiological studies. Transfection experiments in *Plasmodium falciparum* showed that introduction of N86Y into the parasite gene *pfmdr1* confers amodiaquine resistance *in vitro* and this mutation is associated with increased rates of clinical failure after amodiaquine monotherapy [8, 9]. Yet this mutation increases *in vitro* drug sensitivity to lumefantrine. Whereas the mutant allele is more commonly seen in recurrent infections after artesunate-amodiaquine, the wild-type allele is selected after artemether-lumefantrine [10].

Amplification of the *pfmdr1* (wild type) gene is associated with mefloquine resistance [11]. In Cambodia, where mefloquine resistance was widespread, it was observed that as piperazine resistance emerged, sensitivity to mefloquine was restored and prevalent *P. falciparum* strains reversed to a single copy *pfmdr1* genotype [12, 13]. Although this coincided with the decrease in mefloquine drug pressure, the observation that the marker for piperazine resistance (amplification of the *pfplasmepsin2* gene) is rarely detected in conjunction with the marker of mefloquine resistance (amplification of the *pfmdr1* gene) suggests opposing resistance mechanisms [14, 15].

Whether this 'mutual exclusiveness' represents a role of *pfmdr1* in piperazine resistance (for instance by restricting the amount of piperazine entering the food vacuole) or is simply the effect of a relative low mefloquine pressure in the last decade in Cambodia and Vietnam needs further investigation. Importantly, although in low frequency, parasites bearing both markers of mefloquine resistance and piperazine resistance (*pfmdr1* and *pfplasmepsin2-3* amplification, respectively) have been found in field isolates [16], and its prevalence was recently reported to have increased in Preah Vihear province in Cambodia, after the reintroduction of artesunate-mefloquine as first line treatment [17]. The consequence of the double amplification of *pfmdr1* and *pfplasmepsin2-3* for efficacy of the TACT DHA-piperazine-mefloquine has not been established.

An increase in the QTc-interval following intake of the antimalarials piperazine and amodiaquine has been described [18-22]. In the recent TRACII study conducted primarily in adults, we also observed that the QTc interval increased after administration of DHA-piperazine by a mean of around 20 milliseconds. Reassuringly, the addition of mefloquine to DHA-piperazine did not lead to a further increase of the QTc-interval. Further, the incidence of a QTc prolongation following treatment of more than 60 milliseconds was comparable between subjects treated with DHA-piperazine and DHA-piperazine + mefloquine. Data from the TRACII study also confirmed that a treatment with artemether-lumefantrine does not prolong the QTc-interval whereas the addition

of amodiaquine to artemether-lumefantrine prolonged the QTc-interval by about 10 milliseconds over the first 64 hours, which conforms to what has been previously described for amodiaquine. Amodiaquine did not increase the incidence of a QTc-prolongation >60 milliseconds above baseline, which is rare in the treatment with artemether-lumefantrine alone (about 1 in 300 treatments). Any antimalarial treatment is associated with a drop in the heart rate in the first day of treatment. As the fever and/or clinical illness subsides the heart rate generally decreases. The TRACII study confirmed previous findings that amodiaquine use is associated with a bigger decrease in heart rate compared to other antimalarials and a higher incidence of bradycardia (<54 beats/minute), both in adults and children.

